9.4.4.	Drug Misuse.....	47
9.4.5.	HEPATIC FUNCTION ABNOMALITY.....	47
9.4.6.	PREGNANCY.....	47
10.	STATISTICAL CONSIDERATION	48
10.1.	ANALYSIS SET	48
10.1.1.	EFFICACY ANALYSIS SET.....	48
10.1.2.	SAFETY ANALYSIS SET.....	48
10.2.	SAMPLE SIZE AND RATIONALE	49
10.3.	STATISTICAL PARAMETERS AND STATISTICAL ANALYSIS PLAN	49
10.4.	FINAL ANALYSIS	49
11.	ETHICAL AND LEGAL ASPECTS	50
11.1.	GOOD CLINICAL PRACTICE (GCP)	50
11.2.	DELEGATION OF INVESTIGATOR DUTIES	50
11.3.	SUBJECT INFORMATION AND INFORMED CONSENT	50
11.4.	CONFIDENTIALITY	51
11.5.	PROTOCOL AMENDMENTS	51
11.6.	APPROVAL OF THE CLINICAL STUDY PROTOCOLS AND AMMENDMENTS	

11.7.	CLOSURE OF THE STUDY	52
11.8.	FINANCIAL DISCLOSURE	52
12.	Exploratory biomarker studies	52
13.	REFERENCES	53
Appendix A.	56
APPENDIX B.	84
APPENDIX C.	85

Version History

Version Number	Version date	Summary/Reason for changes
1.11	27Oct2017	Appendix C (Add POLE mutation method)
1.12	08Feb2018	Add sites
1.13	14Mar2018	Delete KCSG, contraception period modification Amended Appendix A
1.2	14Jun2018	IC #3 & EC #24, Study period
1.3	21May2019	Amended section 9.4.2 ,change sites & investigators.
1.4	01Dec2020	Amended Appendix A
1.5	11Nov2021	Amended Appendix A (TMG amendment)
1.6	12Apr2022	Added the maximum number of Durvalumab administrations allowed
1.7	12Dec2022	Amended Table 1.Highly effective methods of contraception Added section 9.4.1 to 9.4.4 (Other events requiring reporting; Timeline, Medication error, Drug Abuse, Drug misuse) Amended Appendix A (TMG amendment)

Protocol Synopsis	
Title	A phase II study of durvalumab in patients with mismatch repair deficient or POLE mutated metastatic colorectal cancer
Duration	IRB approval ~ Dec 2023
Investigators	Principal Investigator: [name], Department of Oncology, Asan Medical Center
Objectives	
 ✓ Primary Objective 
 • Objective response rates (RECIST 1.1) ✓ Secondary Objectives 
 • Response rates by irRECIST • Disease control rates • Progression-free survival • Overall survival • Safety and toxicity assessments • Exploratory biomarker studies - Opal Multiplex Tissue Staining with Opal™ including PD-1 and PD-L1
Design	Prospective, open-label, multicenter phase II study
Background	
Later-line therapies after failure of standard treatments for metastatic colorectal cancer patients are limited; regorafenib and TAS-102 have shown clinical activity for these patients, however, efficacy outcomes seemed not to be sufficient although there have been rather higher frequencies of adverse events.
 
Mismatch repair (MMR) deficiency or microsatellite instability-high (MSI-H) played a role of negative predictive factor for adjuvant fluorouracil-based chemotherapy in patients with resected colorectal cancer. In the metastatic setting, deficient MMR or MSI-H represented poor prognosis; however, their predictive role has been documented after the pembrolizumab trial was reported. The results of the pembrolizumab trial demonstrated that the PD-1 blockade with pembrolizumab monotherapy showed 40% of confirmed immune-related objective response rates in patients with MMR deficient metastatic colorectal cancers; hence there was no objective response in those with MMR proficient tumors. The progression-free rates at 20 weeks were 78% versus 11%, respectively, also favouring those with MMR deficient tumors. However, the MMR deficiency of MSI-H is found in only about 5% in patients with metastatic colorectal cancer, which is too small to expand potential candidate of immunotherapy.
 
One of the proposed mechanism of promising efficacy from pembrolizumab for MMR deficient colorectal cancer is that MMR deficient or MSI-H colorectal cancers harbour higher somatic mutation loads than MMR proficient colorectal cancer (a

	
mean of 1782 somatic mutations per tumor in the MMR deficient tumors versus 73 in the MMR proficient tumors in the results of pembrolizumab trial); somatic mutations have the potential to encode non-self immunogenic antigens; therefore, immunotherapy enhancing immune surveillance produced promising treatment efficacy in the MMR deficient tumors.
 
The POLE gene encodes the catalytic subunit of DNA polymerase epsilon, and it involves DNA repair and chromosomal replication. The POLE mutations are located in the exonuclease domain, and their presence has already been reported in the various cancers including colorectal and endometrial cancer.
 
The POLE mutations represent high somatic mutation loads in patients with colorectal cancer, especially in those with MMR proficient or MSS, therefore, tumors harbouring POLE mutations might be susceptible to immune checkpoint blockade. Based on these reasons, we planned a phase II study of durvalumab monotherapy in patients with previously treated, metastatic, MMR deficient (MSI-H) or POLE mutated colorectal cancer.

Patients number
	
The primary endpoint is objective response rate of durvalumab in mismatch repair deficient (microsatellite instable) or POLE mutated metastatic colorectal cancer patients who have progressed after standard therapies.
 
Assuming the target of response rate was set to 30% and a rate of 10% or below was considered futile. A 2-stage optimal design, as proposed by Simon, was used to allow early termination of any ineffective treatment early in the study. With a 1-sided, type I error of 5% and power of 0.8, the planned study was to proceed in 2 steps. In the first step, 10 patients were required, and if complete or partial response was observed in 2 or more patients, the study was to proceed to the second step with 19 additional patients (29 patients as a total). If this condition was not met, the study would be stopped for futility. In the second step, if complete or partial response was observed in 6 or more patients, the treatment will be considered effective. Assuming a dropout rate of 10%, 33 patients were required.


Inclusion criteria
	
 1. Histologically or cytologically confirmed adenocarcinoma of the colon or the rectum. 2. Mismatch repair deficient or microsatellite instable (defined below), or POLE mutated tumors 
 A. Mismatch repair deficient: loss of expression by immunohistochemical stains ≥ 1 out of 4 markers (MLH1, MSH2, MSH6, PMS2) B. Microsatellite instable: loss of stability ≥ 2 out of 5 gene panels (BAT-25, BAT-26, D2S123, D5S346, D17S250) C. POLE gene: P286R mutation or other mutation 3. Refractory to at least one agent of prior treatments (fluoropyrimidines, irinotecan or oxaliplatin) Progressed after at least first-line systemic chemotherapy for

	
metastatic setting (progressed within 6 months after completion of adjuvant chemotherapy is also considered as first-line failure)
 
 4. ≥ 1 measurable lesion(s) by RECIST 1.1. 5. Unresectable advanced or metastatic disease. 6. Age over 20 years old. 7. ECOG performance status of 0-1 or lower. 8. Adequate organ functions. 
 A. Bone marrow function: Hemoglobin ≥ 9.0 g/dL, ANC $\geq 1,500/\text{mm}^3$, platelet $\geq 100,000/\text{mm}^3$ B. Hepatic functions: bilirubin ≤ 1.5 X ULN, AST/ALT ≤ 2.5 X ULN (≤ 5 X ULN in cases of liver metastasis) C. Renal functions: serum Cr ≤ 1.5 X ULN or calculated CCr (Cockroft) > 40 ml/min 9. Be willing and able to comply with the protocol for the duration of the study. 10. Give written informed consent prior to study-specific screening procedures, with the understanding that the patient has the right to withdraw the study at any time, without prejudice. 11. Female subjects must either be of non-reproductive potential (≥ 60 years old and no menses for ≥ 1 year without an alternative medical cause, or history of hysterectomy, or history of bilateral tubal ligation, or history of bilateral oophorectomy) or must have a negative serum pregnancy test upon study entry. 12. Women of childbearing potential and men must agree to use adequate contraception since signing of the IC form until at least 90days after the last study drug administration.

Exclusion criteria
	
 1. Any prior treatment with PD-1 or PD-L1 inhibitor, including durvalumab. 2. Involvement in the planning and/or conduct of the study. 3. Receipt of the last dose of chemotherapy ≤ 28 days prior to the first dose of study drugs. 4. Mean QT interval corrected for heart rate (QTc) ≥ 470 msec calculated from 3 electrocardiograms (ECGs) using Frediricia's Correction. 5. Any unresolved toxicity NCI CTCAE Grade ≥ 2 from previous anticancer therapy with the exception of alopecia, vitiligo, and the laboratory values defined in the inclusion criteria 6. Patients with Grade ≥ 2 neuropathy will be evaluated on a case-by-case basis after consultation with the Study Physician. 7. Patients with irreversible toxicity not reasonably expected to be exacerbated by treatment with durvalumab may be included only after consultation with the Study Physician. 8. Any concurrent chemotherapy, IP, biologic, or hormonal therapy for cancer

	
treatment. Concurrent use of hormonal therapy for non-cancer-related conditions (eg, hormone replacement therapy) is acceptable.
 
9. Current or prior use of immunosuppressive medication within 14 days before the first dose of durvalumab, with the exceptions of intranasal and inhaled corticosteroids or systemic corticosteroids at physiologic doses, which are not to exceed 10 mg/day of prednisolone, or an equivalent corticosteroid.
 
10. Concurrent or previous history of another primary cancer within 3 years prior to randomisation except for curatively treated cervical cancer in situ, non-melanomatous skin cancer, superficial bladder cancer (pTis and pT1) and curatively treated thyroid cancer of any stage. Concurrent, histologically confirmed, unresected thyroid cancer without distant metastasis could be allowed with the agreement of the chief principal investigator.
 
11. Uncontrolled CNS metastases; permitted if asymptomatic or neurologically stable.
 
12. Prior radiation therapy would be permitted, but non-radiated evaluable lesions should be present at study entry.
 
13. Radiation therapy during study treatment is not permitted, but if the local investigator decides that radiation therapy should be given during study treatments, he should be convinced that there is no evidence of disease progression with agreement of the chief principal investigator.
 
14. Congestive heart failure \geq New York Heart Association (NYHA) class 2.
 
15. Unstable angina, new-onset angina within 3 months, or history of myocardial infarction within 6 months before the study entry.
 
16. Active or prior documented autoimmune disease within the past 2 years; subjects with vitiligo, Grave's disease, or psoriasis not requiring systemic treatment (within the past 2 years) are not excluded.
 
17. Active or prior documented inflammatory bowel disease.
 
18. History of prior immunodeficiency.
 
19. History of allogeneic organ transplantation.
 
20. History of hypersensitivity to durvalumab or any excipient.
 
21. Clinical diagnosis of active tuberculosis.
 
22. Receipt of live attenuated vaccination within 30 days prior to study entry.
 
23. Known history of testing positive for HIV
 
24. Hepatitis B virus (HBV) or hepatitis C virus (HCV) infection at screening (positive HBV surface antigen or HCV RNA if anti-HCV antibody screening test positive) Except, resolved HBV infection (as evidenced by detectable HBV surface antibody, detectable HBV core antibody, undetectable HBV DNA, and undetectable HBV surface antigen) or Chronic HBV infection (as evidenced by detectable HBV surface antigen or HBV DNA). Subjects with chronic HBV

--	---

	
infection must have HBV DNA < 100 IU/mL and must be on antiviral therapy.
 
25. Major surgery or significant traumatic injury within 28 days prior to study treatment.
 
26. Non-healing wound, ulcer, or bone fracture.
 
27. Current evidence of significant gastrointestinal bleeding or (impending) obstruction.
 
28. Concomitant participation in another interventional clinical trial.
 
29. Pregnant or breast-feeding subjects. Women of child-bearing potential must have pregnancy test within 7 days and a negative result must be documented before start of study treatment.
 
30. Substance abuse, medical, psychological or social conditions that may interfere with the subject's participation in the study or evaluation of the study results.

Treatment plan
	
The mismatch repair deficient or microsatellite instable, or POLE mutated metastatic colorectal cancer patients who were refractory to fluoropyrimidines, irinotecan and oxaliplatin with or without targeted agents will be accrued.
 
After checking the eligibility for the study entry, patients will be entered into the study treatment with durvalumab monotherapy.
 
Study treatment consists of durvalumab 1500 mg Q4W for patients > 30 kg, and will be repeated every 4 weeks. For patients ≤ 30 kg, weight based dosing of 20 mg/kg durvalumab Q4W will be used.
 
Response evaluation will be performed every 8 weeks (± 1-week window period). Treatment will be continued until disease progression, unacceptable adverse events or the patient's refusal.
 
Treatment through progression is at the investigator's discretion, and the investigator should ensure that patients do not have any significant, unacceptable, or irreversible toxicity that indicate that continuing treatment will not further benefit the patient. The Investigator should ensure that patients still meet all of the inclusion criteria and none of the exclusion criteria for this study.

Statistical consideration
	
All patients who entered into the study will be included for response rates and survival estimation and who received at least 1 cycle of study treatment will be considered as eligible for safety assessment. Descriptive statistics were reported as proportions and medians. Progression-free survival (PFS) and overall survival (OS) were assessed by the Kaplan-Meier method and the 95% confidence interval (95% CI) for the median time to event was computed.


Evaluation
	
Evaluation before study entry (within 2 weeks)
 
 1. Complete medical history. 2. Physical examination including ECOG performance status. 3. Radiologic assessments using RECIST 1.1. (permitted to be assessed within 28 days from the study treatment) 4. CBC with differentials. 5. Serum chemistry: calcium, phosphorus, glucose, BUN, creatinine, total protein, albumin, AST/ALT, alkaline phosphatase, total bilirubin, uric acid and electrolytes. 6. Routine urinalysis 7. Serum CEA 8. Serum TSH, free T4, T3 9. Serum amylase/lipase 10. EKG (3 consecutive EKG for eligibility check) 11. Chest X-rays 12. Urine β-hCG will be performed in women with child-bearing potential. 13. Other tests (i.e. bone scans) if clinically indicated. 
Evaluation during study treatment (every cycle)
 
 1. Physical examination including ECOG performance status and drug-related side effects. 2. CBC with differentials. 3. Serum chemistry: calcium, phosphorus, glucose, BUN, creatinine, total protein, albumin, AST/ALT, alkaline phosphatase, total bilirubin, uric acid and electrolytes. 4. Serum amylase/lipase. 5. Toxicity assessments (NCI-CTC version 4.0) 
Response evaluation (every 8 weeks \pm 1 week window period)
 
 1. Serum CEA, TSH, T3 and free T4 2. CT (or MRI) scans of evaluable/measurable lesions by RECIST 1.1. 3. Other test (i.e. bone scans) if clinically indicated 4. Response evaluation will be performed every 8 weeks without regard to the schedules of study treatment. 
Post-treatment follow-up (every 3 months)
 
 1. Subsequent treatments (chemotherapy, immunotherapy or radiotherapy) and their responses
--------------------------	---

	
2. Survival information on subject3. Status of disease and date of progression (in patients who stopped study treatment without documentation of disease progression)4. Date and cause of death
--	---

연구 계획 요약	
연구 제목	DNA 복구 유전자 결핍 또는 POLE 유전자 돌연변이가 있는 전이성 대장암에서 durvalumab의 효능을 평가하는 2상 연구
연구 기간	IRB 심의일 ~ 2023년 12월
연구자	책임연구자: [name], 서울아산병원 중양내과
연구 목표	
 ✓ 일차 목표 
 • 종양 반응율 (RECIST 1.1 기준) ✓ 이차 목표 
 • irRECIST 에 의한 종양 반응율 • 종양 조절율 (disease control rates) • 무진행 생존 기간 (progression-free survival) • 전체 생존 기간 (overall survival) • 안전성 및 독성 평가 • 탐색적 생체 표지자 연구 
 - Opal Multiplex Tissue Staining with Opal™ including PD-1 and PD-L1
연구 설계	전향적, 공개, 다기관 2상 연구
연구 배경	
표준 치료에 진행한 전이성 대장암의 후기 치료는 제한되어 있다. 후기 치료로 regorafenib과 TAS-102 임상연구 결과가 일부 생존 기간 향상에 도움이 되는 것으로 보고되었으나 그 효과는 아직 불충분하고 일부 심한 독성도 보고되고 있다.
 
DNA 복구 유전자 결핍 (mismatch repair deficiency, dMMR) 또는 현미부수체불안정 (microsatellite instability-high, MSI-H)는 수술적 절제가 시행된 대장암에서 플루오로피리미딘 기반 화학요법의 효과가 없는 음성 예측인자로 알려져 있으며, 전이성 대장암에서는 그 자체가 나쁜 예후를 반영하는 것으로 되어 있다. 그러나 최근 전이성 대장암에서 dMMR 또는 MSI-H가 pembrolizumab의 치료 예측인자로서 역할을 하는 연구 결과가 발표되었다. dMMR/MSI-H 전이성 대장암에서 pembrolizumab을 이용하여 PD-1을 억제하였을 때 종양 반응율이 40%에 달하였다. 반면 DNA 복구 유전자가 정상적으로 발현되는 경우 (mismatch repair proficiency, pMMR)에는 종양 반응율이 0% 였다. 20주 째에 종양이 진행하지 않은 환자의 비율도 78% 대 11%로 dMMR/MSI-H 대장암에서 높았다.
 
dMMR/MSI-H 전이성 대장암이 pembrolizumab 등 면역치료에 반응하는 이론적인 근거 중 하나는, dMMR/MSI-H 전이성 대장암에서 종양 유전자 돌연변이가 매우 많이 발생한다는 것이다. 유전자 돌연변이가 많은 경우 항원에 대한 노출이 많아지기 때문에 면역치료의 역할이 커진다는 이론이다. 실제로 pembrolizumab에 반응하였던 dMMR/MSI-H 대장암 환자의 유전자 돌연변이 개수를 보았을 때 평균 1782개의 종양 유전자 돌연변이가 발견되었다.
 
POLE 유전자 역시 DNA 복구와 염색체 복제 과정에 관여하는 유전자로 알려져 있으며, POLE 유전자 돌연변이가 있는 경우 다른 종양 유전체 돌연변이가 많이

	
발생하는 것으로 보고되어 있다. 즉, pMMR/MSS 대장암에서 POLE 유전자 돌연변이가 있는 경우 dMMR/MSI-H 대장암과 마찬가지로 종양 유전자 돌연변이가 많이 존재하는 것으로 간주할 수 있으며, 이 역시 면역치료의 좋은 대상이 될 수 있다. 위와 같은 배경으로 표준 치료에 진행한 전이성 대장암 중에서 dMMR/MSI-H 또는 POLE 유전자 돌연변이가 있는 환자에서 durvalumab 단독치료의 2상 연구를 계획하였다.

환자 수
	
본 연구의 일차 목표는 dMMR/MSI-H 또는 POLE 유전자 돌연변이가 있는 전이성 대장암 환자에서 durvalumab 단독 치료를 하였을 때의 종양 반응율이다. 목표 종양 반응율을 30%, 10% 미만의 반응율을 보이는 경우 실패하는 것으로 가정하였을 때, Simon 2-stage optimal design에 의하면 1단계에서 10명의 환자 등재 후 2명 이상에서 종양 반응을 보이는 경우 2단계로 진입하고, 2단계에서 추가적으로 19명의 환자를 등재하게 된다 (type I error 5%, power 0.8). 총 29명의 평가 가능 환자가 필요하고, 10%의 탈락율을 고려할 때 총 33명의 환자가 등재된다.


선정 기준
	
 1. 조직학적/세포학적으로 증명된 대장의 선암 2. DNA 복구 유전자 결핍 (dMMR) 또는 현미부수체 불안정 (MSI-H) 또는 POLE 유전자 돌연변이가 있는 경우 
 A. dMMR: 면역조직화학염색 기법으로 MLH1, MSH2, MSH6, PMS2 중 1개 이상 면역단백표현이 없는 경우 (loss of expression) B. MSI-H: PCR 기법으로 5개 유전자 중 (BAT-25, BAT-26, D2S123, D5S346, D17S250) 2개 이상에서 불안정성이 보이는 경우 C. POLE gene: P286R mutation or other mutation 3. 플루오로피리미딘, 옥살리플라틴 또는이리노테칸 중 최소 1가지 이상의 약제에 내성. 전이성 대장암의 치료로 최소한 1차 요법 이상 시행하여 진행한 경우(보조화학요법 종료 후 6개월 이내 임상적 또는 영상학적으로 진행한 경우에도 1차요법 이상에 실패한 것으로 간주) 4. RECIST 1.1. 기준에 따른 계측 가능 (measurable) 병변의 존재. 5. 수술적인 치료가 불가능한 경우 6. 만 20세 이상 7. ECOG 활동도 0-1 8. 적절한 장기 기능 
 A. 골수기능: 혈색소 (Hb) \geq 9.0 g/dL, 호중구 (ANC) \geq 1,500/mm³, 혈소판 (PLT) \geq 100,000/mm³ B. 간기능: bilirubin \leq 정상 상한치의 1.5배, AST/ALT \leq 정상 상한치의 2.5배 (간 전이가 있는 경우 \leq 정상 상한치의 5배) C. 신기능: 혈청 크레아티닌 \leq 정상 상한치의 1.5배 또는 calculated CCr (Cockcroft) $>$ 40 ml/min 9. 연구 기간 동안 연구 계획서에 순응하고 치료 계획에 준수할 의지가 있는 환자. 10. 연구 동의서에 자발적으로 서명하고, 자발적으로 연구에 참여하고 언제든지 참여를 철회할 수 있음을 이해하는 환자.

	
11. 대상자가 여성인 경우 임신 가능성이 없어야 함 (60세 이상이면서 1년 이상 생리가 없었던 경우 또는 자궁적출술 또는 양측난소절제수술을 시행한 경우). 그 외 임신 가능성이 있다면 연구 참여 전에 임신 반응 검사를 시행하여 임신이 아님을 증명하여야 한다.
 
12. 가임기의 남녀 환자의 경우, 연구약 투여 기간 동안과 최종 투여 후 최소한 90일 까지 적절한 피임법을 준수할 수 있는 환자.


제외 기준
	
1. 이전에 durvalumab을 포함한 PD-1 또는 PD-L1 억제제를 사용한 적이 있는 경우.
 
2. 연구 계획 또는 수행에 관계된 종사자
 
3. 마지막 화학요법 시행 후 28일이 지나지 않은 경우
 
4. QTc \geq 470 msec 이상인 경우 (3회의 EKG 시행 후 평균 값, Frediricia's Correction)
 
5. 이전 항암요법으로부터 해결되지 않은 CTCAE 2등급 이상인 독성 (탈모, 백반증, 선정기준에 적합하지 않은 실험실검사 결과 제외)
 
6. 2등급 이상의 신경병증 환자의 경우 대상자 질환에 대한 평가는 연구자의 의학적 자문 이후 진행한다.
 
7. 비가역성 독성 환자에서 durvalumab 치료가 증상을 더 악화하지 않을 경우에는 연구자의 의학적 판단을 기준으로 한다.
 
8. 항암 치료를 위해 화학요법, 시험약, 생물학적 제제, 또는 호르몬 요법을 현재 사용하는 환자. 암과 무관한 상태에 대한 호르몬 요법의 동시 사용(예: 호르몬 대체 요법)은 허용된다.
 
9. 14일 이내의 면역 억제제 사용, 단 흡입성 스테로이드나 생리적 용량의 스테로이드는 허용한다 (10 mg/day of prednisolone 또는 equivalent dose의 다른 스테로이드 제제).
 
10. 3년 이내에 다른 원발암의 병력이 있는 경우, 단 수술적으로 완치된 표재성 자궁 경부암, 표재성 피부암 (흑색종 제외), 표재성 방광암 (pTis, pT1)과 4기를 제외한 갑상샘암은 허용된다. 갑상샘암의 경우 수술적인 제거가 되지 않았더라도 연구자의 판단 하에, 전이성 대장암의 치료 경과와 예후에 영향을 주지 않는다는 연구자의 판단이 있다면, 총 책임 연구자와 상의 후 환자를 연구에 참여시킬 수 있다.
 
11. 조절되지 않은 중추신경계 전이.
 
12. 이전의 방사선 치료 병력은 허용된다. 그러나 방사선 조사 범위에 들어가지 않는 평가 가능 병변의 존재가 있어야 한다.
 
13. 원칙적으로 연구 치료 기간 동안의 방사선 치료는 허용되지 않는다. 그러나 연구자가 질병진행의 증거가 없는 치료병변 외의 부위에 방사선 치료가 필요하다고 판단되는 경우 총 책임연구자와 상의 후 진행 할 수 있다.
 
14. New York Heart Association (NYHA) class 2 이상의 심부전.
 
15. 3개월 이내의 불안정성 협심증 병력, 또는 최근의 새로 생긴 심근 허혈 증상, 또는 6개월 이내의 심근 경색 병력이 있는 경우.
 
16. 2년 이내의 활동성 자가면역질환, 단 전신 치료가 필요하지 않는 vitiligo, 그레이브스씨 병, 건선은 허용된다.

	
 17. 염증성 장질환의 병력 18. 면역억제의 병력 19. 장기 이식 환자 20. Durvalumab 또는 비슷한 약제에 대한 과민반응 21. 연구 참여 시 활동성 결핵이 있는 경우 22. 생백신 (live attenuated vaccine) 투여 후 30일 이내 23. HIV 감염 병력 또는 알려진 면역결핍 синдром. 24. 스크리닝 단계에서 활동성HBV/HCV 감염(HBV 표면항원양성 또는 HCV RNA 양성). 단, 회복된B형간염(anti HBs 와 anti HBc가확인되고, HBsAg, HBV DNA가 검출되지 않는 경우) 또는 HBsAg, HBV DNA로 확인된 만성 B형 간염의 경우 제외. 만성 B형 간염의 경우 항바이러스제 치료 중이며, HBV DNA <100IU/mL 임을 반드시 확인해야 한다. 25. 연구 시작 28일 이내의 주요 수술 또는 심각한 외상 병력. 26. 치유되지 않은 창상, 궤양 또는 골절. 27. 위장관 출혈이 지속되거나, 장 폐색이 의심되는 경우. 28. 현재 다른 약물이 투여되는 임상 연구에 참여 중인 경우. 29. 임신부 또는 모유 수유 중인 환자. 가임기의 여성은 연구 참여 7일 이내에 임신 반응 검사를 시행하여야 하며 음성임이 확인되어야 한다. 30. 연구 참여와 연구 결과 해석에 지장을 줄 수 있다고 판단되는 약물 남용자, 내과적/정신과적/사회적 질환을 가진 자.
치료 계획	
이전의 표준 치료 (플루오로피리미딘, 옥살리플라틴, 이리노테칸)에 불응하며, DNA 복구 유전자 결핍 (mismatch repair deficiency) 또는 현미부수체불안정 (microsatellite instability) 또는 POLE 유전자 돌연변이가 있는 전이성 대장암 환자를 대상으로 한다.
 
선정/제외 기준에 만족하는 경우만 연구에 참여할 수 있으며, durvalumab은 1500 mg의 용량으로 매 4주 마다 반복한다.
 
반응 평가는 매 8주 마다 (\pm 1주) 시행되며, 질병의 진행, 감내할 수 없는 독성 또는 동의 철회가 있을 때 중지한다. 반응 평가는 연구 치료의 주기와 상관 없이 매 8주 마다 시행한다.
 
질병의 진행 이후에도 연구자의 판단 하에 durvalumab을 지속할 수 있으며, 이때는 감내할 만한 부작용이 없는지, 환자에게 이득이 되는지, 그리고 그 시점에서의 환자 상태가 선정/제외 기준에 부합하는지 평가 후 진행하여야 한다.

통계학적 고려	
연구에 참여한 모든 환자는 유효성 (반응율) 분석에 포함될 것이며, 안전성 평가에는 1차 이상 연구 약제를 투여 받은 환자가 포함될 것이다. 통계 기술은 %와 중간값으로 기술되며, 생존 기간 (PFS, OS)은 Kaplan-Meier 기법을 이용하여 분석/비교될 것이다.

연구 절차	
연구 참여 전 절차 (연구 치료 시작 2주 이내)

	
 1. 병력 확인. 2. ECOG 활동도를 포함한 신체 검진. 3. RECIST 1.1 기준에 따른 계측 가능 병변 확인 4. 일반혈액검사 (CBC) 5. 혈청 일반화학검사 (Chemistry): calcium, phosphorus, glucose, BUN, creatinine, total protein, albumin, AST/ALT, alkaline phosphatase, total bilirubin, uric acid and electrolytes. 6. 요검사 7. 혈중 CEA 8. 갑상선 기능 검사 (TSH, T3, free T4) 9. 혈중 amylase/lipase 10. 심전도 (3회 시행) 11. 흉부 X-선 검사 12. 가임기 여성의 경우 임신 반응 검사 (소변 beta-hCG) 13. CT, MRI 등의 영상학적 검사 외에 연구자가 반응 평가에 필요하다고 판단하는 다른 검사 
연구 치료 기간 동안의 절차 (매 연구 치료 시작 전)
 
 1. 신체 검진, ECOG 활동도 검사, 약제 복용 확인 2. 일반혈액검사 (CBC). 3. 혈청 일반화학검사 (Chemistry): calcium, phosphorus, glucose, BUN, creatinine, total protein, albumin, AST/ALT, alkaline phosphatase, total bilirubin, uric acid and electrolytes. 4. 혈중 amylase/lipase 5. 독성 및 안전성 평가 (NCI-CTC version 4.0) 
반응 평가 (매 8주 마다 ± 1 week window period)
 
 1. 혈중 CEA, 갑상선 기능 검사 (TSH, T3, free T4), 2. 영상의학적 검사를 통한 종양 계측/반응 평가 (RECIST 1.1) 3. 그 외 연구자가 반응 평가를 위해 필요하다고 판단하는 검사 4. 반응 평가는, 연구 치료의 주기와 상관없이 매 8주 (± 1주)마다 시행되어야 한다. 
치료 종료 후 절차 (매 3개월 마다)
 
 1. 이후 치료에 대한 정보 (항암화학요법, 면역요법, 방사선치료): 기간, 반응, 약제 종류 등 2. 생존에 대한 정보 3. 질병의 확인 없이 연구 치료가 종료된 경우, 질병의 진행을 확인할 수 있는
--	--

	정보 4. 사망한 경우, 사망일과 사망 원인
--	-----------------------------

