3.3. FIXED DOSING

A population PK model was developed for durvalumab using monotherapy data from a Phase 1 study (*study 1108; N=292; doses= 0.1 to 10 mg/kg Q2W or 15 mg/kg Q3W; solid tumors*). Population PK analysis indicated only minor impact of body weight (WT) on PK of durvalumab (coefficient of ≤ 0.5). The impact of body WT-based (10 mg/kg Q2W) and

fixed dosing (750 mg Q2W) of durvalumab was evaluated by comparing predicted steady state PK concentrations (5th, median and 95th percentiles) using the population PK model. A fixed dose of 750 mg was selected to approximate 10 mg/kg (based on median body WT of ~75 kg). A total of 1000 patients were simulated using body WT distribution of 40–120 kg. Simulation results demonstrate that body WT-based and fixed dosing regimens yield similar median steady state PK concentrations with slightly less overall between-subject variability with fixed dosing regimen.

Similar findings have been reported by others.²⁴⁻²⁷ Wang and colleagues investigated 12 monoclonal antibodies and found that fixed and body size-based dosing perform similarly, with fixed dosing being better for 7 of 12 antibodies.²⁵ In addition, they investigated 18 therapeutic proteins and peptides and showed that fixed dosing performed better for 12 of 18 in terms of reducing the between-subject variability in pharmacokinetic/pharmacodynamics parameters.²⁶

A fixed dosing approach is preferred by the prescribing community due to ease of use and reduced dosing errors. Given expectation of similar pharmacokinetic exposure and variability, we considered it feasible to switch to fixed dosing regimens. Based on average body WT of 75 kg, a fixed dose of 1500 mg Q4W durvalumab (equivalent to 20 mg/kg Q4W) is included in the current study. Fixed dosing of durvalumab is recommended only for subjects with > 30kg body weight due to endotoxin exposure. Patients with a body weight less than or equal to 30 kg should be dosed using a weight-based dosing schedule (Appendix B).

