7.2. DOSE AND TREATMENT REGIMEN

Patients (> 30 kg in weight) will receive 1500 mg of durvalumab via intravenous infusion every 4 weeks. Patients (≤ 30 kg in weight) will receive weight based dosing of 20 mg/kg durvalumab via intravenous infusion every 4 weeks.

Durvalumab treatment can be continued up to the 36-cycle dosing. After 36 cycles of treatment, durvalumab should be discontinued.

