7.3. DOSE MODIFICATION AND DELAYS

7.3.1. GENERAL RULES FOR DOSE MODIFICATION AND DELAYS

- Dose modification (reduction or escalation) is not allowed.
- Dose delays in case of clinically meaningful events are permitted; however, study treatment should be discontinued in case of 4 weeks delays.
- All the response evaluation procedures including CT scans should be performed as planned in patients with treatment delay without regard to the cycles of study treatment. Dose delays, reasons for treatment delay, actions to be taken and outcome will be recorded in patient chart and CRF.
- Regarding the adverse events, dose delays could be made under investigators' discretion.
- When the study treatment is restarted, the investigator should ensure that AE is recovered \leq grade 1 or there is no safety risk for the patients.
- Prophylactic use of G-CSF (or GM-CSF) or erythropoietin is not allowed.

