APPENDIX B.

Durvalumab weight based dose calculation

For durvalumab dosing done depending on subject weight. Weight-based dosing should be utilized for patients ≤ 30 kg:

1. Cohort dose: X mg/kg
2. Subject weight: Y kg
3. Dose for subject: XY mg = X (mg/kg) \times Y (kg)
4. Dose to be added into infusion bag:

$$\text{Dose (mL)} = \text{XY mg} / 50 \text{ (mg/mL)}$$

where 50 mg/mL is durvalumab nominal concentration.

The corresponding volume of durvalumab should be rounded to the nearest tenth mL (0.1 mL). Dose adjustments for each cycle are only needed for greater than 10% change in weight.

5. The number of vials required for dose preparation is the next greatest whole number of vials from the following formula:

$$\text{Number of vials} = \text{Dose (mL)} / 10.0 \text{ (mL/vial)}$$

Example:

1. Cohort dose: 20 mg/kg
2. Subject weight: 30 kg
3. Dose for subject: 600 mg = 20 (mg/kg) \times 30 (kg)
4. Dose to be added into infusion bag:

$$\text{Dose (mL)} = 600 \text{ mg} / 50 \text{ (mg/mL)} = 12.0 \text{ mL}$$

5. The number of vials required for dose preparation:

$$\text{Number of vials} = 12.0 \text{ (mL)} / 10.0 \text{ (mL/vial)} = 2 \text{ vials}$$

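### The Korean synopsis gives durvalumab 1500 mg with no weight condition, while the rest of the protocol confines that dose to patients above 30 kg; separately, 7.3.1 and Appendix B disagree on adjusting a weight-based dose

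*Combined protocol and SAP*

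**What the plan says.** **Dose by weight.** The treatment plan in the Korean synopsis reads "durvalumab은 1500 mg의 용량으로 매 4주 마다 반복한다": 1500 mg, repeated every 4 weeks. It mentions neither body weight nor a weight-based alternative.

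The English synopsis gives 1500 mg above 30 kg and adds: "For patients ≤ 30 kg, weight based dosing of 20 mg/kg durvalumab Q4W will be used". Section 7.2 makes the same split: "Patients (> 30 kg in weight) will receive 1500 mg of durvalumab via intravenous infusion", and "Patients (≤ 30 kg in weight) will receive weight based dosing of 20 mg/kg durvalumab via intravenous infusion every 4 weeks". Section 7.1 ties its preparation instruction for 1500 mg to patients above 30 kg and sends lighter patients to Appendix B, which calls for weight-based dosing at or below 30 kg. Section 3.3 gives the reason: "Fixed dosing of durvalumab is recommended only for subjects with > 30kg body weight due to endotoxin exposure".

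**Changing the dose.** Section 7.3.1 states: "Dose modification (reduction or escalation) is not allowed". It makes no exception for body weight. Appendix B, within its weight-based calculation, states: "Dose adjustments for each cycle are only needed for greater than 10% change in weight".

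**Related facts.** Section 6.1 sets no minimum weight and requires age over 20. The schedule in Section 8.1 records weight at screening, every cycle and end of treatment. Section 7.2 does not say whether entry or current weight decides the dosing scheme.

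**The concern.** The Korean synopsis is current protocol text. It is a full parallel synopsis (objectives, eligibility, treatment, procedures) in a trial led from a Korean centre, so site staff could reasonably take it as operative. Its treatment plan does not point to Section 7.2 or Appendix B. For a patient at or below 30 kg it leads to a different dose from the rest of the protocol, and the limit it omits is one that Section 3.3 links to a safety reason.

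The second issue concerns a patient already on weight-based dosing whose weight changes by more than 10%. Appendix B then provides for a new dose, while the wording of 7.3.1 allows none. Two sites could follow the protocol and dose the same patient differently.

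**Working it through.** **Inputs.** Weight-based dose 20 mg/kg and fixed dose 1500 mg (English synopsis, 7.2); concentration 50 mg/mL and 10.0 mL per vial (7.1, Appendix B); adjustment threshold 10% (Appendix B).

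**Formulas.** Dose = 20 × weight. Volume = dose / 50. Vials = volume / 10, rounded up. Ratio = 1500 / (20 × weight).

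**The plan's own figures reproduce.** At 30 kg: 20 × 30 = 600 mg; 600 / 50 = 12.0 mL; 12.0 / 10 = 1.2, so 2 vials, as in Appendix B. The fixed dose is 1500 / 50 = 30.0 mL, as in 7.1, and 1500 / 75 = 20 mg/kg at the 75 kg average weight used in 3.3.

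**Korean synopsis against the rest.** At or below 30 kg:

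| Weight (kg) | Weight-based dose (mg) | Korean synopsis (mg) | Korean synopsis (mg/kg) | Ratio |
|---|---|---|---|---|
| 30 | 600 | 1500 | 50.0 | 2.50 |
| 29 | 580 | 1500 | 51.7 | 2.59 |
| 27 | 540 | 1500 | 55.6 | 2.78 |
| 25 | 500 | 1500 | 60.0 | 3.00 |

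Only the 30 kg row uses a weight worked through in the protocol; the others are assumed, to show the range. Because the ratio rises as weight falls, 2.5 is its minimum for anyone at or below 30 kg.

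**Section 7.3.1 against Appendix B.** Take a patient on weight-based dosing who falls from 30 to 26.9 kg (an assumed example). The change is (30 − 26.9) / 30 = 10.3%, just above the threshold. Appendix B gives 20 × 26.9 = 538 mg; 7.3.1, read literally, keeps 600 mg. The difference is 62 mg, and 62 / 600 = 10.3% of the starting dose.

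**Crossing 30 kg by 10% or less.** From 29 to 31 kg the change is 2 / 29 = 6.9%. 7.3.1 and the 10% rule in Appendix B both leave the dose at 580 mg. Section 7.2 gives 1500 mg only if read on current weight; read on entry weight it also leaves 580 mg. From 31 to 29 kg (2 / 31 = 6.5%), 7.3.1 keeps 1500 mg, as does 7.2 on entry weight; 7.2 on current weight gives 580 mg.

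**The case against.** **The Korean synopsis is only a summary.** It is abbreviated elsewhere too; for example, its sample size paragraph drops the second-stage threshold of 6 responses. A site preparing a dose would work from 7.1, where the 30.0 mL instruction is tied to patients above 30 kg, and the operative sections all carry the split. This lowers the chance of a dosing error. It does not remove the contradiction, because the Korean sentence states a dose and leaves out the condition on it.

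**Hardly anyone is affected.** Patients must be over 20, and the dosing simulation in 3.3 used weights of 40 to 120 kg. This stands and is the main reason to rate the point minor.

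**7.3.1 can be read together with Appendix B.** Its other items deal with delays, adverse events and growth factors, so it may bar only toxicity-driven changes. Recalculating milligrams for weight leaves the assigned 20 mg/kg unchanged. This is a fair reading, but the text does not say so.

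**A stronger reading that the documents do not support.** A reader might infer that 7.2, 7.3.1 and Appendix B prescribe conflicting doses whenever a patient crosses 30 kg, so that one patient could be given doses about 2.6-fold apart. The differing dose appears only if 7.2 is read on current weight, which 7.2 does not say. Applying the 10% rule to a patient leaving the fixed dose is also an interpretation, since the rule sits in the calculation for patients at or below 30 kg. The 2.6 itself needs an assumed 29 kg patient. What is shown at a crossing is that the protocol is silent.

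**Conclusion.** The point holds as a minor internal inconsistency. The Korean synopsis omits the 30 kg condition that the English synopsis, 3.3, 7.1, 7.2 and Appendix B apply; this needs no interpretation. The difference is 2.5-fold at 30 kg and larger below it.

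The conflict between 7.3.1 and Appendix B is literal but small (about 10% of the dose in the example), and it disappears if 7.3.1 is meant only for toxicity. The silence of 7.2 on entry or current weight is a missing detail.

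The documents do not say how many patients would weigh 30 kg or less; that few if any of 33 adults would do so is an assumption. None of these doses enters the response-rate endpoint or the two-stage sample size calculation. No view is taken on which dose or rule is right.

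**What to change.** 1. Reconcile the treatment plan of the Korean synopsis with the English synopsis, 3.3, 7.1, 7.2 and Appendix B.
2. Reconcile 7.3.1 with Appendix B by stating whether recalculation for weight falls under the ban on dose modification.
3. As a clarification only, state in 7.2 whether entry or current weight decides the dosing scheme.

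The sponsor decides which rule holds in each case. The cost is about one sentence in each of three places. No new data are needed, because weight is already recorded every cycle, and the statistical sections do not change.
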